6.2.1 Adverse Events by Baseline Characteristics

AE[†]s (as described below) will be reported (n %) for the following baseline characteristics in the safety set and safety per protocol set :

- Age group (2-23 months, 2-10, 11-18, 19-34, 35-55, 55-64)
- Children group (<18, ≥18)
- Gender (male, female)
- Past diagnosis (yes, no)

	CONFIDENTIAL :	Last Update Date
	THIS DOCUMENT AND INFORMATION CONTAINED HEREIN IS PROPRIETARY TO COMPANY AND IS NOT TO BE DISCLOSED WITHOUT THE WRITTEN PERMISSION OF COMPANY.	20-APR-2018
STATISTICAL ANALYSIS PLAN(V6.0)		

- Temperature location (axillary, oral, rectal, ear)
- Administration site (left deltoid, right deltoid, left thigh, right thigh, other)
- Concomitant medication (yes, no)
- Kidney disorder (yes, no)
- Liver disorder (yes, no)
- Pregnancy (yes, no)
- Number of previous Menveo (0, 1, 2, 3)
- Study vaccination number (1, 2, 3, 4)

The n(%) of AEs[†] and its 95% confidence interval will be calculated using the normal approximation and analyzed using χ^2 - test. If more than 20% of expected frequencies of the cell counts are less than 5, Fisher’s exact test will be used instead of the chi-square test.

† AE : AE includes solicited and unsolicited AE (DAY 1-7), medically attended AE (DAY 1-29) and SAE (DAY 1-29).

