2.1 Safety Set

Table 2.1.1 Summary of AE

Safety set	No. subjects with AE n (%)	95% CI† for the percentage of subjects with AE (Lower , Upper)	No. AEs n	No. subjects with ADR n (%)	95% CI† for t percentage o subjects with A (Lower , Upp
Solicited AE (2-23 months)					
Local AE					
Systemic AE					
Solicited AE (2-5 years)					
Local AE					
Systemic AE					
Solicited AE (≥ 6 years)					
Local AE					
Systemic AE					

Safety set	No. subjects with AE n (%)	95% CI† for the percentage of subjects with AE (Lower ,Upper)	No. AEs n	No. subjects with ADR n (%)	95% CI† for the percentage of subjects with ADR (Lower ,Upper)	No. ADR n	Total n (%)
Unsolicited AE							
SAE							
MAAE							
Death							
Total							

† 95% CI will be calculated using the normal approximation.

* Day 1-7: Solicited AE, Unsolicited AE

* Day 1-29: SAE, Death

* Day 8-29: MAAE

Table 2.1.2 Summary of AE by Age (month, year)

Safety Set	No. subjects with AE	No. AEs	Total	p-value
	n (%)	n	n (%)	
2-23 months				X ² -test or Exact test
2-10				
2-5				
6-10				
11-18				
19-34				
35-55				
> 55				
Total				

Table 2.1.3 Summary of AE by Age (month, year)

Safety Set	No. subjects with AE	No. AEs	Total	p-value
	n (%)	n	n (%)	
Solicited AE				X ² -test or Exact test
2-23 months				
2-10				
2-5				
6-10				
11-18				
19-34				
35-55				
> 55				
Solicited Local AE				X ² -test or Exact test
2-23 months				
2-10				
2-5				
6-10				
11-18				
19-34				

Safety Set	No. subjects with AE n (%)	No. AEs n	Total n (%)	p-value
35-55 > 55				
Solicited Systemic AE 2-23 months 2-10 2-5 6-10 11-18 19-34 35-55 ≥56				X ² -test or Exact test
Unsolicited AE 2-23 months 2-10 2-5 6-10 11-18 19-34 35-55 ≥56				X ² -test or Exact test
SAE 2-23 months 2-10 2-5 6-10 11-18 19-34 35-55 ≥56				X ² -test or Exact test
MAAE 2-23 months 2-10 2-5				X ² -test or Exact test

Safety Set	No. subjects with AE n (%)	No. AEs n	Total n (%)	p-value
6-10				
11-18				
19-34				
35-55				
≥56				
ADR				
2-23 months				
2-10				
2-5				
6-10				X ² -test or Exact test
11-18				
19-34				
35-55				
≥56				
Death				
2-23 months				
2-10				
2-5				
6-10				X ² -test or Exact test
11-18				
19-34				
35-55				
≥56				

Table 2.1.4 Summary of AE by Children group

Safety Set	No. subjects with AE n (%)	No. AEs n	Total n (%)	p-value
< 18 years				
≥ 18 years				X ² -test or Exact test
Total				

Table 2.1.5 Summary of AE by Gender

Safety Set	No. subjects with AE n (%)	No. AEs n	Total n (%)	p-value

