In case the Diary Card is not retrieved within 10 days after Day 29, subject or subject’s parent/legal representative will be contacted by phone to assess the occurrence of adverse events, determine the subject’s clinical status and complete study termination. All information will be recorded by the site staff on the subject’s medical record and collected in the appropriate section of the CRF.

All SAEs will be monitored until resolution and/or the cause is identified. If a SAE remains unresolved at study termination, a clinical assessment will be made by the investigator and the GSK regional physician to determine whether continued follow up of the SAE is needed.

Table 3.1-1: Safety Assessment Table

Medical History: All significant past diagnoses including all allergies, major surgeries requiring inpatient hospitalization, other significant injuries or hospitalizations, any conditions requiring prescription or chronic medication (i.e., >2 weeks in duration), or other significant medical conditions based on the investigator’s judgment.
	
From birth, collected at clinic visit Day 1

---	--

	CONFIDENTIAL :	Last Update Date
	THIS DOCUMENT AND INFORMATION CONTAINED HEREIN IS PROPRIETARY TO COMPANY AND IS NOT TO BE DISCLOSED WITHOUT THE WRITTEN PERMISSION OF COMPANY.	20-APR-2018
STATISTICAL ANALYSIS PLAN(V6.0)		

Immediate reactions: Subjects will be assessed for immediate hypersensitivity reactions.
	For at least 30 minutes after vaccination

Solicited local adverse events: < 6 years : injection site erythema, injection site induration, injection site tenderness ≥ 6 years : injection site erythema, injection site induration, injection site pain
	Days 1-7 after vaccination

Solicited systemic adverse events: < 6 years : change in eating habits, sleepiness, irritability, rash, vomiting, diarrhea, fever ≥ 6 years : chills, nausea, malaise, generalized myalgia, generalized arthralgia, headache, rash, fever
	Days 1-7 after vaccination
All unsolicited AEs will be collected	Days 1-7 after vaccination

Medically attended Adverse Events: Events that require a physician's visit or an emergency room visit (events that are managed by telephone or means other than a face-to-face evaluation by a clinician do not qualify as medically attended AEs).
	From Day 1 to study termination (Day 29/early termination)

Serious AEs: All SAEs will be collected.
	From Day 1 to study termination (Day 29/early termination)

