6.2.2. Analysis of Solicited AE

Frequencies and % of subjects experiencing each adverse event will be presented for each symptom severity. Summary tables showing the occurrence of any local or systemic reaction overall and at each time point will also be presented (see Appendix 1 Table 4.1.3 and 4.2.3).

Post-vaccination adverse events reported from Day 1 to Day 7 will be summarized by maximal severity. The severity of local adverse events for subjects < 6 years of age will be categorized as follows. Injection-site erythema and induration: absent (0 to 9 mm), mild (10 to 25 mm), moderate (26 to 50 mm), severe (> 50 mm); injection-site tenderness: none, mild (minor light reaction to touch), moderate (cried or protested to touch), severe (cried when injected limb was moved). For subjects \geq 6 years, injection-site erythema and induration absent (1 to 24 mm), mild (25 to 50 mm), moderate (51 to 100 mm), severe (>100 mm); pain: none, mild (present but does not interfere with activity), moderate (interferes with activity), severe (prevents daily activity).

For subjects \geq 6 years of age, the severity of systemic adverse events (i.e., chills, nausea, malaise, generalized myalgia, generalized arthralgia, headache) occurring up to 7 days after each vaccination will be categorized as none, mild (present but not interfering with daily activity), moderate (some interference with daily activity), and severe (prevents daily activity) except for rash, which will be

	CONFIDENTIAL :	Last Update Date
	THIS DOCUMENT AND INFORMATION CONTAINED HEREIN IS PROPRIETARY TO COMPANY AND IS NOT TO BE DISCLOSED WITHOUT THE WRITTEN PERMISSION OF COMPANY.	20-APR-2018
STATISTICAL ANALYSIS PLAN(V6.0)		

categorized as none, urticarial, or other.

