7.4 Additional Analyses for DDS (Data Disclosure Shell)

- Frequency and percentage by Age group (2-23 months, 2-10, 11-18, 19-64)
- Frequency and percentage by study termination and reason not completed
- Incidence proportion and the number of Non-SAE
- The number of death resulting from AE (frequency and percentage)
- Incidence proportion and number according to the preferred terms of Non-SAE (frequency and percentage)

7.5 Additional Analyses for AE in the Local Product Label (Unsolicited AE Day 1-29)

- Preferred terms of Serious AE/ADR, unexpected AE/ADR will be presented respectively according to the proportion.

	CONFIDENTIAL :	Last Update Date
	THIS DOCUMENT AND INFORMATION CONTAINED HEREIN IS PROPRIETARY TO COMPANY AND IS NOT TO BE DISCLOSED WITHOUT THE WRITTEN PERMISSION OF COMPANY.	20-APR-2018
STATISTICAL ANALYSIS PLAN(V6.0)		

8. Notes

- Each statistical analysis will be carried out with SAS Software version 9.4 or more recent version.
- In the descriptive statistics, mean, SD, minimum, median, and maximum will be calculated for continuous variables, and frequency and percentage for categorical variables.
- Data including sign of inequality such as “ ≥ 20 ”, “ > 20 ” will be excluded from analysis.
- All test statistics will be the results of two-sided tests with the statistical significant level of 0.05.
- The followings shall be included only in re-examination report:
 - Analysis by type of concomitant medications
 - Item ② of paragraph 6.2.3
 - Estimation of 95% confidence interval for incidence proportion of AEs by background factors
 - Paragraph 6.3, 6.4

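### Age p-values for pooled and solicited AEs in SAP V6.0 cross age 6, where the checklist and mm cuts change, so they cannot be attributed to age

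*SAP*

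**What the plan says.** All references are to SAP V6.0 unless stated.

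- **Test.** Section 6.2.1 compares AE incidence over "Age group (2-23 months, 2-10, 11-18, 19-34, 35-55, 55-64" and over under 18 versus 18 and over. It uses chi-square; when expected counts are small, Fisher's "exact test will be used instead of the chi-square test". The Notes (section 8) add: "All test statistics will be the results of two-sided tests with the statistical significant level of 0.05".
- **Outcome.** The footnote to 6.2.1 reads "AE includes solicited and unsolicited AE (DAY 1-7), medically attended AE (DAY 1-29) and SAE (DAY 1-29", so solicited events are in the tested outcome.
- **Checklists.** Table 3.1-1 in section 2.4 gives the under-6 systemic list as "change in eating habits, sleepiness, irritability, rash, vomiting, diarrhea, fever". From 6 years the list is chills, nausea, malaise, myalgia, arthralgia, headache, rash and fever. The third local item is tenderness below 6 and pain from 6.
- **Size grading.** For erythema and induration, section 6.2.2 uses "absent (0 to 9 mm), mild (10 to 25 mm), moderate (26 to 50 mm), severe (> 50 mm" below 6 years. From 6 years it has "injection-site erythema and induration absent (1 to 24 mm), mild (25 to 50 mm", with higher cuts above that.
- **Table shells.** The latest shells in the supplied text are those of V4.0, Appendix 1. Tables 2.1.2 and 2.1.3, both titled "Summary of AE by Age (month, year", carry all-age p-values. Table 2.1.3 has separate ones for solicited, solicited local and solicited systemic AEs.

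**The concern.** A test across age bands asks whether incidence is the same at every age, which requires the same event to be counted at every age. Here the instrument changes at the sixth birthday. A 15 mm erythema is mild in a 5-year-old and absent in a 6-year-old. Sleepiness is prompted for below 6 and headache from 6. The 2-10 band and the under-18 group each mix both definitions, and nothing in 6.2.1 aligns the outcome or limits the comparison.

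A significant p-value could then be reported as an age effect of the vaccine when part or all of it comes from the form. The reverse can also happen: the definitions could hide a real difference. The data were gathered to describe safety by age, so a reader will look at these p-values.

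**Working it through.** **1. The plan's own figure.** Section 2.2 expects 3,000 evaluable subjects aged 2-55 years and 600 aged 2-23 months: 3,600 × 1.10 = 3,960, the stated enrolment. No event rate, effect size or power is given for the age test, so the rates below are assumptions.

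**2. Overlap of the definitions.**

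| | Under 6 years | 6 years and over |
|---|---|---|
| Local items | 3 | 3 |
| Systemic items | 7 | 8 |
| Total | 10 | 11 |
| Erythema/induration graded mild from | 10 mm | 25 mm |

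The two lists share four items: erythema, induration, rash and fever.

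**3. Rejection probability with no true age effect.** Let the rate be p from age 6 and p + x below it, where x is purely definitional. For bands of size n_i with rates p_i and pooled rate p̄, the k-band chi-square has noncentrality

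λ = Σ n_i (p_i − p̄)² / [p̄(1 − p̄)], with k − 1 degrees of freedom.

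The 2-23 month band is 600, as in section 2.2. The 55-64 band is set to zero because it lies outside eligibility. Three splits of the 3,000 are assumed (2-5 / 6-10 / 11-18 / 19-34 / 35-55):

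- A: 150/150/900/900/900
- B: 30/70/900/1,500/500
- C: 300/300/800/800/800

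Worked case: split A, p = 5%, x = 2 points, 2-10 as one band.

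- Band rates are 7%, 6%, 5%, 5%, 5%; the 6% is the average of 150 at 7% and 150 at 5%.
- p̄ = (42 + 18 + 45 + 45 + 45)/3,600 = 195/3,600 = 0.0542.
- Σ n_i (p_i − p̄)² = 0.1504 + 0.0102 + 3 × 0.0156 = 0.2075 (unrounded terms).
- λ = 0.2075/0.05123 = 4.05. Against the critical value 9.488 on 4 df, the test rejects with probability 0.32 instead of 0.05.

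| Base rate p | Shift x | 2-10 as one band, splits A-C | 2-10 divided at 6, with 600 aged 2-5 (600/300/700/700/700) |
|---|---|---|---|
| 5% | 2 points | 0.315-0.324 | 0.43 |
| 5% | 5 points | 0.98 | 0.997 |
| 40-50% | 2 points | 0.093-0.098 | 0.11-0.12 |
| 40-50% | 5 points | 0.395-0.427 | 0.57-0.58 |

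The last column is the high end, with 1,200 subjects under 6. Under split B with 2-10 divided, the extra degree of freedom slightly lowers the figures (0.30, 0.98, 0.09, 0.38-0.39). At a 50% base, a shift of the same size in the other direction gives the same result.

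**4. The mm cuts alone.** Suppose 5% of subjects have lesions of 25 mm or more at every age. If *any* means above the absent category, the shift x is the share with lesions of 10-24 mm. Rejection is then 0.11 at 1%, 0.32 at 2%, 0.64-0.65 at 3% and 0.98 at 5%. If *any* means above 0 mm, x = 0 and rejection stays at 0.05. Section 6.2.2 says each event will also be split none/any but does not define none in mm. The V4.0 shells (Tables 4.1.1 to 4.1.3) give 0-9 mm and 1-24 mm their own column, so the question is open.

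**5. Does the test also respond to age?** With no definitional shift and assumed true rates of 45/45/50/45/40% over the five bands, power is 0.86-0.95. Restricted to 11-18, 19-34 and 35-55, which share one definition set, a 50/45/40% gradient is detected with power 0.92-0.98.

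**The case against.** A reader might infer that these p-values test the definitions and not age, or that significance is to be expected whatever the vaccine does. The documents do not support either reading.

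- All bands from 11 years up share one checklist and one set of cuts, and step 5 shows that the test responds to real age differences.
- A two-group contrast of under 6 against 6 and over on erythema/induration alone gives striking numbers. With 700-1,200 under 6 and a 5% base, rejection exceeds 99% for a 5-point excess and is 55-68% for a 2-point excess. The plan runs neither that outcome nor that contrast. In a composite, a 10-24 mm lesion adds a case only if the subject has no other event.
- An event missing from a checklist can still be reported as unsolicited on Days 1-7, so in the pooled outcome the difference is one of prompting.
- Much of the separation is already planned. V4.0 Table 2.1.1 reports solicited events separately for 2-23 months, 2-5 years and 6 years and over, with confidence intervals. Tables 2.1.2 and 2.1.3 show 2-5 and 6-10 as rows.
- Protocol 7.1 makes every analysis descriptive. The age groups in the supplied protocol 7.6 (11-18, 19-34, 35-55) all use one checklist. No decision rests on these p-values, and the age-specific checklists were introduced on purpose.

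All of this stands, and it limits the size and weight of the point. It does not remove the point: section 6.2.1 still tests across age 6 an outcome that is defined differently on each side, and prompted and unprompted reporting are not equivalent.

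**Conclusion.** The point holds for pooled AEs, and for solicited AEs if the V4.0 layout was kept, wherever the comparison crosses age 6. Those p-values confound age with definition and cannot be attributed to age. Comparisons among bands from 11 years up are sound.

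The size cannot be fixed from the documents. On the assumptions in the working, false rejection runs from about 9-12% (2-point shift, 40-50% base) to 98% or more (5-point shift, 5% base), against a nominal 5%. The mm-cut part depends on the undefined none/any rule; the checklist part does not, but its size and direction are unknown. The V6.0 shells are not in the supplied text, so only the pooled-AE test is established from V6.0 itself. This is a moderate defect of interpretation: the descriptive within-checklist estimates are not affected.

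**What to change.** 1. For pooled and solicited AEs, run age tests only within under 6 years (2-23 months versus 2-5 years) and within 6 years and over (6-10, 11-18, 19-34, 35-55). Alternatively, show these outcomes by age without p-values, which is simpler and fits protocol 7.1.
2. In 6.2.1, divide the 2-10 band into 2-5 and 6-10, as the V4.0 shells already do.
3. Drop the under-18 versus 18-and-over p-value for these outcomes.
4. State in mm what counts as none and as any for erythema and induration in each age group. The scale from 6 years starts its absent category at 1 mm, so 0 mm also needs a place.
5. Keep all-age comparisons for SAEs, medically attended AEs, fever and rash. Read the all-age unsolicited AE p-value with caution: vomiting and diarrhea are solicited only below 6 and headache only from 6, so such events change class at that age.
6. Compare erythema and induration across all ages at a common cut of 25 mm or more only if raw millimetres were recorded, because 25 mm lies inside the under-6 mild category.

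The cost is SAP wording and some re-cut tables, and the single all-age p-value for any AE is lost. Items 1 to 5 need no new data.

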Infant from 2 to 23 months of age may enroll if scheduled to receive MenACWY-CRM prophylaxis as part of vaccination series per routine standard of care. The infant may enroll at any point, for one injection only, in the vaccination series, including those subjects who may have already initiated the vaccination series.

Rational for changes: Text has been added to clarify the procedure of infant vaccination.

CHANGE 2 (Section 3.3)

Previously reads:

A physical exam/assessment, including height, weight and body temperature (preferably axillary) will be performed and results recorded before vaccination.

Now reads:

A physical exam/assessment, including height, weight and body temperature (preferably axillary **for subjects from 2 to 55 years of age and tympanic for infants**) will be performed and results recorded before vaccination.

Rational for change: Inclusion of infants in standard temperature measurement.

CHANGE 3 (Section 4.2, Exclusion Criteria)

Previously reads:

NA

Now reads:

1. Infants who were already enrolled in this trial for previous vaccination.

Rational for change: To ensure that infants are not enrolled more than once.

CHANGE 4 (Section 6.2.5, Post Study Event)

Previously reads:

Any AE that occurs outside the protocol-specified observation period or after the end of the study but considered to be caused by the study vaccine must be reported to NVD. These AEs will be processed by the NVD Pharmaco-vigilance group.

Now reads:

Any AE that occurs outside the protocol-specified observation period or after the end of the study but considered to be caused by the study vaccine must be reported to the sponsor as spontaneous report as per the local practice.

Rational for change: Spontaneous reporting to be applied to this PMS studies.

CHANGE 5 (Section 6.2.6)

Previously reads:

Pregnancy data must be recorded on a Pregnancy Report CRF (initial report) and Pregnancy Follow-Up CRF (outcome report) and reported to NV.

Now reads:

Pregnancy data must be recorded on a Pregnancy Report CRF (initial report) and Pregnancy Follow-Up CRF (outcome report) and reported to study CRO.

Rational for change: Procedure correction involving the CRO instead of NVD.

CHANGE (Section 7.0, Statistical Plan)

Previously reads:

NA

Now reads:

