The statistical plan to analyze and report data according to ICH requirement is described in the following section. A separate document will describe the statistical analysis plan (including population for analysis) according to MFDS.

Rational for change: To clarify that additional SAP will be performed to follow ICH requirements.

Table 1: Other Changes

CHANGE	LOCATION(S) OF CHANGE	RATIONALE FOR CHANGE

Change in the location of the injection including infants.
 
Menveo is to be administered as a single 0.5 ml intramuscular injection, preferably into the anterolateral aspect of the thigh in infants or into the deltoid muscle (upper arm) in children, adolescents and adults.
	
Synopsis
 
Section 3.3
 
Section 5.1
 
Section 5.4
	
Alignment with study population

Change in the study population, adding infants from 2 to 23 months.
	
Study title
 
Synopsis
 
Section 1; 2 ; 3.1; 3.2; 4.1; 7.2; 7.6
	
Approval by KFDA

Novartis

Document Approval Certificate /

PPD

The individuals listed have approved this document for implementation using an electronic signature in the Atlas EDMS. / PPD

UserName: PPD

Title: Cluster Physician

Date: Tuesday, 28 October 2014, 13:46 GMT

Meaning: As an approver, I agree with the content and format of this document.

=====

This signature certificate is only valid when accompanied by all the pages of the document. /

PPD

CLINICAL STUDY PROTOCOL V59_62

A Multicenter Post Marketing Surveillance Study to Monitor the Safety of Novartis Meningococcal ACWY Conjugate Vaccine (MenACWY-CRM) Administered According to the Prescribing Information to Healthy Subjects from 2 months to 55 Years of Age in the Republic of South Korea

Amendment Number 3

Revised Protocol version 4.0 issued on 12 May 2015

The present amendment reflects changes to the Protocol version 3.0

issued on 22 OCT 14

Property of Novartis Vaccines

Confidential

May not be used, divulged, published or otherwise disclosed without written consent of Novartis Vaccines.

The purpose of this amendment is to implement changes requested by Korean Health Authorities.

DESCRIPTION OF CHANGE(S) AND RATIONALE:

CHANGE 1

In the synopsis section, page 4, 3rd paragraph, following text was added.

For subjects 2-23 months of age, the parents will also be asked to consent for surveillance after subsequent vaccinations.

CHANGE 2 (PAGE 23, SECTION 3.3.2)

Previously read:

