Male				X ² -test or Exact test
Female				
Total				

Table 2.1.6 Summary of AE by Past diagnosis

Safety Set	No. subjects with AE n (%)	No. AEs n	Total n (%)	p-value
Yes				X ² -test or Exact test
No				
Total				

Table 2.1.7 Summary of AE by Temperature Location

Safety Set	No. subjects with AE n (%)	No. AEs n	Total n (%)	p-value
Axillary				X ² -test or Exact test
Oral				
Rectal				
Ear				
Total				

Table 2.1.8 Summary of AE by Administration Site

Safety Set	No. subjects with AE n (%)	No. AEs n	Total n (%)	p-value
Left Deltoid				X ² -test or Exact test
Right Deltoid				
Left Thigh (Infant only)				
Right Thigh (Infant only)				
Other				
Total				

Table 2.1.9 Summary of AE by Concomitant medication

Safety Set	No. subjects with AE n (%)	No. AEs n	Total n (%)	p-value
Yes				X ² -test or Exact test
No				
Total				

Table 2.1.10 Summary of AE by Kidney Disorder

Safety Set	No. subjects with AE n (%)	No. AEs n	Total n (%)	p-value
Yes				X ² -test or Exact test
No				
Total				

Table 2.1.11 Summary of AE by Liver disorder

Safety Set	No. subjects with AE n (%)	No. AEs n	Total n (%)	p-value
Yes				X ² -test or Exact test
No				
Total				

Table 2.1.12 Summary of AE by Pregnancy

Safety Set	No. subjects with AE n (%)	No. AEs n	Total n (%)	p-value
Yes				X ² -test or Exact test
No				
Total				

Table 2.1.13 Summary of AE by Number of previous MenACWY

Safety Set	No. subjects with AE n (%)	No. AEs n	Total n (%)	p-value
0				X ² -test or Exact test
1				
2				
3				
Total				

Table 2.1.14 Summary of AE by Study vaccination number

Safety Set	No. subjects with AE n (%)	No. AEs n	Total n (%)	p-value
1				

Safety Set	No. subjects with AE n (%)	No. AEs n	Total n (%)	p-value
2				X ² -test or Exact test
3				
4				
Total				

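### The unstratified p-values for AE incidence by temperature location and administration site are confounded by age and cannot separate route or site from age

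*SAP*

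**What the plan says.** SAP V6.0, section 6.2.1, lists the factors by which AE incidence is reported in the Safety Set and the Safety per Protocol Set. Two of them are "Temperature location (axillary, oral, rectal, ear" and "Administration site (left deltoid, right deltoid, left thigh, right thigh, other". One testing rule covers every factor on the list: a chi-square test, replaced by Fisher's exact test under the condition "If more than 20% of expected frequencies of the cell counts are less than 5". Section 8 (Notes) adds "All test statistics will be the results of two-sided tests with the statistical significant level of 0.05". No age-stratified or age-adjusted version is planned.

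The outcome is a composite. The footnote to 6.2.1 reads "AE includes solicited and unsolicited AE (DAY 1-7), medically attended AE (DAY 1-29) and SAE (DAY 1-29".

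Protocol Amendment 2 links both factors to age:

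- **Temperature route (Change 2).** The pre-vaccination reading is preferably axillary "for subjects from 2 to 55 years of age and tympanic for infants".
- **Injection site (Table 1).** The injection is given "preferably into the anterolateral aspect of the thigh in infants or into the deltoid muscle (upper arm) in children, adolescents and adults".

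In Appendix 1 of SAP V4.0, the AE table by administration site (Table 2.1.8) labels its thigh rows "Left Thigh (Infant only" and has a p-value column. The V6.0 appendix shells are not in the text available for review, so for V6.0 the evidence is the rule in 6.2.1.

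**The concern.** A test of AE incidence across injection sites or temperature routes reads as a statement about site or route. Here the levels of both factors are largely a proxy for age group. Any real difference in AE incidence between infants and older subjects carries straight into these two tables.

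The outcome is also measured differently by age. The Safety Assessment Table in SAP section 2.4 gives seven solicited systemic items under 6 years and eight from 6 years, with only rash and fever in common. Section 6.2.2 grades erythema or induration of 10 to 25 mm as mild under 6 years, but treats 1 to 24 mm as absent from 6 years. A 12 mm reaction is thus mild in a five-year-old and absent in a seven-year-old. This matters most for a comparison of injection sites.

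At stake is a safety report for the regulator that shows a significant result under a site or route heading when the data show only an age or checklist difference.

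**Working it through.** **Group sizes.** SAP section 2.2 plans about 3,960 subjects, to give about 3,000 evaluable at 2 to 55 years and 600 at 2 to 23 months with 10% drop-out. The plan's total is 3,600 × 1.10 = 3,960. (Read the other way, 3,960 × 0.90 = 3,564, close to 3,600.) I use 600 and 3,000.

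**Assumptions.** The documents give no AE rates and no split of site or route by age, so all of these are assumed. In the site illustration every infant is injected in the thigh and every older subject in the deltoid, left and right are equally split in each group, the *other* category is empty, and site has no effect within age.

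**Site test as planned (four occupied levels, 3 df).** Because left and right have equal rates, the Pearson statistic reduces to

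χ² = (p₁ − p₂)² / [p̄(1 − p̄)(1/600 + 1/3,000)], where 1/600 + 1/3,000 = 0.002.

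It is referred to 3 df, since the plan keeps left and right as separate levels. The older group is at 40% (1,200 of 3,000).

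| Infant incidence | p̄ | χ² | p (3 df) |
|---|---|---|---|
| 45% | 1,470/3,600 = 0.4083 | 0.0025/(0.2416 × 0.002) = 5.17 | 0.16 |
| 50% | 1,500/3,600 = 0.4167 | 0.0100/(0.2431 × 0.002) = 20.57 | 1.3e-4 |
| 60% | 1,560/3,600 = 0.4333 | 0.0400/(0.2456 × 0.002) = 81.45 | 1.5e-17 |

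The smallest expected cell count is about 122 (300 × 0.4083), so the chi-square branch of the rule applies.

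**Temperature location when the link to age is imperfect.** Compare ear with axillary, with no route effect within age. The probability that the unstratified test rejects at 0.05 (noncentral chi-square) is:

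| Ear use, infants / older | AE 40% vs 30% | AE 35% vs 30% |
|---|---|---|
| 100% / 0% | 0.998 | 0.678 |
| 90% / 2% | 0.988 | 0.568 |
| 80% / 10% | 0.861 | 0.335 |
| 80% / 30% | 0.453 | 0.153 |
| 60% / 30% | 0.203 | 0.088 |

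With equal AE rates it is 0.05 throughout. With only 100 infants at 40% versus 30%, it runs from 0.572 (100%/0%) down to 0.057 (60%/30%).

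**Effect of stratifying.** In 4,000-replicate simulations of the two-route comparison, a Cochran-Mantel-Haenszel (CMH) test stratified by infants versus 2 to 55 years rejected in 4.7% to 5.6% of runs in all five scenarios. The unstratified test rejected in 46.7% to 98.8% of runs in the four scenarios where AE rates differed by age.

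**Limit of stratifying.** If the thigh is used only in infants and every infant receives it there, no age stratum contains both thigh and deltoid. No stratified test can then compare them; only left versus right can be compared.

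**The case against.** The strongest reply is that little depends on these tables. Protocol section 7.1 makes all analyses descriptive with no null hypothesis. The SAP nowhere says that the breakdowns estimate a site or route effect. AE incidence is also tabulated and tested by age group under the same section, so an age gradient will be visible. All of this stands and limits the impact, but it does not remove the confounding from the two p-values.

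Four stronger readings are tempting, and the documents do not support them:

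- **That age fixes route and site.** Both passages of Amendment 2 state a preference. Older subjects may have ear readings and infants may have other routes; only the thigh rows are labelled for infants alone. The rejection probabilities above fall quickly as the link weakens.
- **That infants have a different checklist from everyone else.** The checklists and size thresholds change at 6 years, so infants share theirs with children aged 2 to 5. Measurement differences enter only across the 6-year boundary.
- **That the tests say nothing about route or site.** They mix the two with age. Left versus right deltoid is not fixed by age, and a true 5-point route difference with no age effect would be detected with probability 0.68 to 0.88 for the three patterns of ear use examined (90%/2%, 80%/10%, 80%/30%).
- **That V4.0 introduced the test when infants were added.** Section 6.2.1 of V1.0 to V3.0 already applied a chi-square or Fisher test to the whole list. Only the p-value column in these two tables was new in V4.0.

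Collapsing site to thigh versus deltoid would also exaggerate the illustration. On 1 df, 45% versus 40% gives p = 0.02, but the planned test keeps left and right separate and gives 0.16.

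**Conclusion.** The point holds as a limited one. The unstratified p-values for temperature location and administration site are confounded by age and, across the 6-year boundary, by different solicited checklists and size thresholds. They cannot separate route or site from age.

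The size depends on two things the documents do not give: the difference in AE incidence between age groups, and how closely route and site follow age. Under complete separation, a 5-point difference need not reach significance in the planned site test (p = 0.16), whereas differences of 10 and 20 points would be strongly significant. With equal AE rates there is no inflation.

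The impact is minor: no stated objective or decision rests on these p-values. The correction is still worth making, because they add little to the age-group table and invite a wrong reading.

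**What to change.** The simplest change in SAP section 6.2.1 is to exempt temperature location and administration site from the testing rule, and to report n (%) with the 95% confidence interval and no p-value for these two factors.

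If tests are wanted, carry them out within age strata (2-23 months, 2-5 years, 6 years and over):

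- **Temperature location:** an age-stratified CMH test.
- **Administration site:** left versus right thigh in infants and left versus right deltoid in older subjects, with a statement that thigh versus deltoid is not separable from age.

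The cut at 6 years matches the change in checklists and thresholds. Either option costs a few lines of SAP text and matching table shells. Age is already recorded, so no new data are needed.
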